1.2 Primary objective

1.2.1 To evaluate the effect of an ALERT specialist on retention in care, based on time to LTFU.

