9.3 Randomization and Stratification

Once eligibility and consent are confirmed and the baseline survey is completed, randomization will occur using the web-based CFAR BIT data management system. Participants will be randomized (1:1) to either the ALERT Enhanced Retention Intervention Arm or the SOC Arm by the study coordinator or ALERT specialist.

We will stratify randomization by whether the patient is a new HIV diagnosis or a prior diagnosis returning to care and by HIV primary care clinic site.

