9.4 Sample Size and Accrual

9.4.1 Power and Sample Size Justification

The primary outcome for this study is to compare the time to LTFU. A secondary outcome is time to initiation of ART. Sample size calculations were based on a two-sided, two-sample log-rank test to compare the differences in time to the-primary endpoint proportions between the intervention arm and the standard of care arm.

Since attrition is a component of the composite endpoint, attrition rates are not used as an adjustment in the power calculations. Assuming 150 subjects per group in each of the two

Table 5: Power based on a two-sided, log-rank test with alpha=0.05 and N=150 per arm (total N = 300)							
Composite	Composite rate	Corresponding	Statistical				
rate without	without	Hazard Ratio	Power (%)				
Endpoint in	Endpoint in	(HR)					
SOC (%)	Intervention						
	(%)						
65	80	1.93	82				
65	85	2.65	97				
70	85	2.19	87				
75	87.5	2.15	78				
75	90	2.73	92				
80	92.5	2.86	87				
80	95	4.35	97				

groups (for a total of 300 subjects), we have 87% power to detect a difference of 15%, assuming a time without a composite endpoint rate of 70% in SOC arm and that the intervention arm will increase the time without an endpoint (to a rate to 85%). This corresponds to a hazard ratio of 2:19. Table 5 shows other possible standard of care rates between arms (and hazard ratios), and corresponding statistical power. The calculations assume that the hazard rates are proportional.

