9.6 Analyses

9.6.1 Statistical Analysis Plan

In general, analyses will incorporate the intent-to-treat principle, namely, all randomized participants will be included in the analysis. The primary analysis compares the ALERT Intervention to the SOC arm. For all secondary analyses of interest, no adjustments for multiple comparisons will be made, and a p-value of 0.05 will be considered statistically significant. Demographic and baseline measurement variables will be summarized via standard descriptive statistics.

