9.6.2 Analysis of Primary Outcome

A survival analysis of "time to LTFU" will be conducted. LTFU is defined as no visit with a prescribing HIV provider in the last 180 days. Time-to-LTFU will be calculated as total days between the first visit and the date when the participant reaches the definition of LTFU.

For example, a subject has his first visit on Jan 1, 2013, and another visit on Mar 1, 2013. If the subject does not have any visits thereafter, or does not have any visits until >180 days later, the subject will be counted as reaching the primary endpoint of LTFU. In this case, the subject would be LTFU if no visit occurred before Aug 27, 2013, (which is 180 days past Mar 1st). The "time-to-LTFU" will be the time period between Jan 1, 2013 and Aug 27, 2013.

At the end of the study, patients who have not reached the primary endpoint will be censored at the time of their last quarterly data extraction.

Patients who meet the primary endpoint and are found to be incarcerated will be removed from the study and censored effective at the time of their incarceration. Those who are incarcerated but return to care upon release, prior to reaching a primary endpoint, will be allowed to remain in study. Patients who change care provider to an external health facility (such as a different clinic system or a nursing facility) will be assessed for their current engagement in care; those who have completed a clinic visit with a prescribing clinician within the 180 days will be considered engaged in

care, and will not be considered LTFU. If possible, these patients will continue to come in for annual study visits.

The null hypothesis is that the median time-to-LTFU estimated using the Kaplan-Meier method will be identical in both groups. The log-rank test will be used to test the null hypothesis against the alternate hypothesis that the median time-to-LTFU is not the same between the groups.

In addition, to assess the factors associated with time-to-LTFU, Cox regression models will be performed on two subgroups, looking at each arm separately. The model will have time to LTFU as the outcome, baseline variables such as demographic, socioeconomic, psychosocial factors, risk behavior, substance use and psychiatric illness as predictors.

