Randomization will be stratified by clinic site and whether the subject is newly diagnosed or returning to care. A total of 300 subjects (150 per arm) will be randomized and followed for a minimum of 48 weeks. SOC will be the clinic standard.

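### Section 9.6.2 frames the log-rank null as equal medians, does not say whether the test uses the randomisation strata, and plans no between-arm effect estimate with a confidence interval

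*Combined protocol and SAP*

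**What the plan says.** The primary objective (section 1.2) is "To evaluate the effect of an ALERT specialist on retention in care, based on time to LTFU". Section 9.6.1 adds: "The primary analysis compares the ALERT Intervention to the SOC arm".

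For that comparison, section 9.6.2 states: "The null hypothesis is that the median time-to-LTFU estimated using the Kaplan-Meier method will be identical in both groups". The log-rank test is to be set against "the alternate hypothesis that the median time-to-LTFU is not the same between the groups". The section then turns to predictors of LTFU: "Cox regression models will be performed on two subgroups, looking at each arm separately". It closes by restating the design: "Randomization will be stratified by clinic site and whether the subject is newly diagnosed or returning to care". Section 9.3 says the same.

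Section 9.4.1 powers a two-sided, two-sample log-rank test with 150 per arm and notes: "The calculations assume that the hazard rates are proportional". A hazard ratio appears only there. No confidence interval is planned anywhere in the supplied text. Section 9.6.3 repeats the median null, the log-rank test and the within-arm Cox models for time to ART.

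Section 9.0 refers to a SAP that gives the detail and overrides section 9. The file contains no SAP text beyond section 9.

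**The concern.** There are three linked points, the first being the main one.

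- **No effect estimate.** The objective is to evaluate an effect, but the planned output for the arm comparison is a p-value and two medians. A Cox model fitted in one arm has no treatment term, so the within-arm models cannot supply a between-arm hazard ratio. Readers would learn whether ALERT helped, but not from any pre-specified estimate by how much.
- **Mismatched null.** The log-rank test does not in general test equality of medians. Two curves can share a median and differ elsewhere, or differ in median and cross. Medians are also a weak summary if most patients in both arms are still in care at the end of follow-up.
- **Strata named but not used.** The trial randomises by site and by new or returning status, yet nothing says whether the primary test is stratified by them. That leaves the choice open until after the data are seen.

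**Working it through.** **Inputs.** From section 9.4.1: 150 per arm, two-sided alpha 0.05, endpoint-free rates 70% (SOC) and 85% (ALERT), hazard ratio 2.19 (SOC to ALERT, so above 1 favours ALERT), power 87%. From the Schema: at least 48 weeks of follow-up, continuing until the last patient reaches 48 weeks. From sections 4.1.6 and 9.3: 3 sites × 2 patient types = 6 strata. Assumptions: the Table 5 rates apply at 48 weeks (no time point is given). Accrual length and stratum risks are not given either, so ranges are shown.

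**The plan's own figure.** HR = ln 0.70 / ln 0.85 = 2.195. Events = 150 × 0.30 + 150 × 0.15 = 67.5. Freedman power = Φ(√67.5 × 1.195/3.195 − 1.96) = 86.7%, which matches the stated 87%. The power calculation is not in question.

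**What a p-value leaves open.** SE(log HR) = √(1/events SOC + 1/events ALERT); SE(difference) = √(p₁q₁/150 + p₂q₂/150). At 70/85% these are √(1/45 + 1/22.5) = 0.258 and √(0.21/150 + 0.1275/150) = 0.0474. If the observed rates equal those shown:

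| SOC / ALERT | HR (95% CI) | Difference, points (95% CI) |
|---|---|---|
| 70 / 80% | 1.60 (1.01 to 2.54) | 10 (0.3 to 19.7) |
| 70 / 85% | 2.19 (1.32 to 3.64) | 15 (5.7 to 24.3) |
| 65 / 80% | 1.93 (1.23 to 3.02) | 15 (5.0 to 25.0) |
| 80 / 95% | 4.35 (1.95 to 9.68) | 15 (7.7 to 22.3) |

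The first row is only just significant (z = 1.99 for log HR). The last three rows show the same 15-point gain with hazard ratios from 1.93 to 4.35, so neither scale alone conveys the effect.

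**Are the medians reached?** Median = d + (48 − d) × ln 2 / (−ln S) weeks, where no event can occur before week d.

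| Model | SOC (S = 0.70) | ALERT (S = 0.85) |
|---|---|---|
| d = 25.7: day 180, clock from first visit (9.6.2) | 69 | 121 |
| d = 17.1: day 120, clock from baseline (9.2), entry 60 days after first visit (6.2.2) | 77 | 149 |
| d = 0: constant hazard | 93 | 205 |

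All exceed 48 weeks. The chance that the Kaplan-Meier median is reached (10,000 simulated trials per cell, follow-up uniform over the stated span, range over the three models) is:

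| Follow-up | SOC | ALERT |
|---|---|---|
| 48 weeks for all | 0% | 0% |
| 48–72 weeks | 7–57% | 0–1% |
| 48–96 weeks | 50–99% | 1–8% |
| 48–144 weeks | 99–100% | 7–81% |

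**Effect of stratifying.** Simulation used 60,000 trials per cell, 6 strata of 50, 1:1 allocation within each stratum, and censoring at 48 weeks. The spread is the ratio of highest to lowest stratum risk. Power is unstratified vs stratified.

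| Spread | Power, marginal rates 70/85% | Power, HR 2.19 within strata | Type I error, unstratified |
|---|---|---|---|
| none | 88.6 vs 88.5% | 88.7 vs 88.6% | 4.9% |
| 4-fold | 89.0 vs 89.8% | 87.8 vs 88.7% | 4.5% |
| 9-fold | 89.8 vs 91.8% | 86.7 vs 89.1% | 3.4% |
| 20-fold | 90.9 vs 94.3% | 84.1 vs 89.3% | 2.6% |

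A separate, smaller simulation (3,000 trials per scenario, stratum log-hazards with SD 1.0) gave type I error of 2.5% unstratified and 5.2% stratified, so stratifying brings the test back to about its nominal level. With follow-up of 48–96 weeks, power is at least 94.7% throughout. The gain is then 0.2–0.3 points at 4-fold, 0.7–1.2 at 9-fold and 1.8–3.5 at 20-fold, and unstratified type I error is 4.0%, 3.1% and 1.8%.

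**The case against.** The strongest reply is that section 9 is only a summary. A hazard ratio with its interval, and the stratification of the test, are details a SAP would carry, and section 9.0 gives the SAP precedence. This stands as a limit: what can be shown is that the supplied text plans no estimate, not that none exists. The median null is a different matter, because it is written in section 9.6.2 and needs correcting whatever another document says.

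The median wording changes no p-value. Under the proportional hazards assumed in section 9.4.1, equal medians and equal survival coincide, so the test is valid and only its hypothesis is misstated. That is conceded.

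Follow-up will exceed 48 weeks for some patients: the Schema keeps early enrollees on study, and section 9.6.4 lists HIV RNA and CD4 at years 1 and 2. The SOC median may therefore be reached. At 48–96 weeks the ALERT median still is in only 1–8% of trials, so a contrast of medians would probably not be available. At 48–144 weeks the range is too wide to conclude either way.

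The unstratified test matches the one that was powered, any error is conservative, and the documents give no basis for 9- or 20-fold spreads. All of that stands, so stratification is the smallest of the three points.

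Kaplan-Meier curves would also let someone derive a retention difference later. That is true, but the time point and method would then be chosen after the results are known.

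**Conclusion.** The concern holds on the supplied text. The primary comparison has a valid test, but its hypothesis is misstated and it has no pre-specified answer to how much ALERT improves retention. A significant result could mean a 10-point gain with an interval starting at 0.3, or a 15-point gain with one starting at 5.7.

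If Table 5 gives 48-week rates, medians cannot fill the gap at the minimum follow-up, and the ALERT median is unlikely to be reached unless follow-up runs well past 96 weeks.

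Leaving out the strata costs 0 to 0.9 points of power up to a 4-fold spread in risk, about 2.0 to 2.4 at 9-fold and 3.4 to 5.2 at 20-fold, with everyone censored at 48 weeks. It makes the test conservative and does not inflate the type I error.

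These figures rest on the 48-week reading of Table 5, the assumed accrual spans, and equal strata with assumed risks. The absence of a planned estimate does not depend on any of them. The change should be made, but the trial's validity is not at risk.

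**What to change.** In section 9.6.2:

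- State the null as equal LTFU-free survival functions in the two arms.
- Specify the primary log-rank as stratified by site and by new or returning status, with a pre-specified rule for merging sparse strata.
- Report the between-arm hazard ratio with 95% CI from a Cox model stratified by the same factors.
- Report Kaplan-Meier LTFU-free proportions at 48 weeks by arm, with their difference and 95% CI.
- Give medians descriptively, only where reached.

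In section 9.6.3, make the same changes to the null, the test and the hazard ratio for time to ART. The point about unreached medians is not made there, because no ART rates are given. If a separate SAP already contains these items, bring section 9.6 into line with it.

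The cost is wording and a little more analysis, with no new data or patients. The one drawback is the need for the merging rule: 67.5 expected events over 6 equal strata is about 11 per stratum, and real strata will be unequal.

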trial to evaluate the effectiveness of a clinic-based HIV Active Linkage, Engagement, and Retention to Treatment (ALERT) specialist on improving endpoints of retention in care and maintenance of antiretroviral therapy (ART) as compared to the current standard of care (SOC) in HIV primary

care clinics.

Duration: Each subject will receive follow-up of at least 48 weeks. Follow-up for

enrolled patients will continue until the last enrolled patients has been

on study for 48 weeks

Sample Size: A total of 300 subjects will be randomized, 150 per arm.

Study Population: Eligible subjects will include 1) newly diagnosed HIV-infected individuals

entering primary HIV care at one of the CCTG clinics, or 2) previously diagnosed HIV-infected individuals who are "out of care" defined as having no visit with a prescribing HIV provider in the last 180 days and

not on a stable ARV regimen.

Stratification: Subjects will be stratified based on study site and if they are newly

diagnosed or returning to care. (See Diagram 1)

Intervention: Subjects will be randomized (1:1) to either the ALERT Enhanced Retention

Intervention Arm or the SOC Arm. Subjects placed into the ALERT Intervention Arm will receive aggressive engagement efforts by the ALERT specialist to ensure visit continuity and retention into care. The ALERT specialist will also administer an education intervention consisting of 5 retention modules designed to improve HIV knowledge and self-efficacy, and will also monitor health care visits and intervene via

methods to track, find, and re-engage patients during the study. Patients placed into the SOC arm will receive the HIV care clinic's current standard

[figure not shown]
of care retention services.

Outcomes:

Primary Outcome: Time to "lost to follow up" (LTFU) defined as the time from study entry to

no visit with a prescribing HIV provider in the last 180 days

DIAGRAM 1: CCTG 594 STUDY SCHEMA

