9.6.3 Analysis of Secondary Outcomes

Main Secondary Outcome: The CCTG 594 secondary outcome is time to initiation of ART. A survival analysis of time to initiation of ART will be conducted. Time to initiation of ART will be calculated as total days between the first visit to the ART start date. For those participants who do not start ART, the time to initiation of ART will be censored to the participant's last visit date.

The NULL hypothesis is that the median time to initiation of ART estimated using the Kaplan-Meier method will be identical in both groups. The log-rank test will be used to test the null hypothesis against the alternate hypothesis that the median time to initiation of ART is not the same between the groups.

In addition, to assess the factors associated with time to initiation of ART, Cox regression models will be performed on two subgroups, looking at each arm separately. The model will have time to initiation of ART as the outcome, baseline variables such as demographic, socioeconomic, psychosocial factors, risk behavior, substance use and psychiatric illness as predictors.

9.6.4 Other Secondary Analyses

Descriptive analyses will be conducted for all the secondary analyses including comparisons between randomized groups on the following measures:

- Baseline and follow-up scores on HIV and health literacy assessments, disclosure rates, adherence, and measures of selfefficacy
- Number of primary care visits per year
- HIV RNA < 50 and <200 copies/mL at years 1 and 2
- CD4 cell counts and changes from baseline in CD4 at years 1 through 2
- Scores on Beck Depression Index
- Substance use
- HIV high-risk transmission behaviors
- Time to AIDS diagnosis or death
- Reasons eligible patients decline study participation

For patients who meet the primary endpoint (LTFU) but subsequently return to care, secondary analyses will measure the proportion returning in the intervention vs. SOC arm and the time between their last and return visit with a prescribing provider.

Fisher's exact test will be used for categorical variables; T-test (or Wilcoxon Rank Sum test, if parametric assumptions fail) will be used for continuous variables.

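### Randomization is stratified by clinic site and new/returning status, but the analyses in Section 9 use neither the strata nor the baseline scores: valid tests, with an optional and nearly free efficiency gain left unused

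*Combined protocol and SAP*

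**What the plan says.** **Design.** The Schema states: "Subjects will be stratified based on study site", together with newly diagnosed or returning status. Section 9.3 repeats it: "We will stratify randomization by whether the patient is a new HIV diagnosis or a prior diagnosis returning to care", and by clinic. So does the analysis section, at the end of 9.6.2: "Randomization will be stratified by clinic site and whether the subject is newly diagnosed or returning to care". Section 4.1.6 names three clinics, so there are 3 × 2 = 6 strata.

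**Time-to-event analyses.** Section 9.6.2 gives the primary test: "The log-rank test will be used to test the null hypothesis against the alternate hypothesis that the median time-to-LTFU" is not equal in the two arms. Section 9.6.3 uses the same test for the main secondary outcome, "against the alternate hypothesis that the median time to initiation of ART is not the same between the groups". Neither names strata or covariates. The only Cox models serve to find predictors: "Cox regression models will be performed on two subgroups, looking at each arm separately". Section 9.4.1 matches the unstratified plan: "Sample size calculations were based on a two-sided, two-sample log-rank test".

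**Continuous outcomes.** Objective 1.3.4 compares the arms on questionnaire scores and CD4. The surveys are taken at entry (6.2.2) and repeated yearly (6.2.4). Section 9.6.4 calls the analyses descriptive but names tests: "T-test (or Wilcoxon Rank Sum test, if parametric assumptions fail) will be used for continuous variables". CD4 is also listed as change from baseline. Section 9.6.1 sets 0.05 as the significance level for all secondary analyses.

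**Precedence.** Section 9.0 describes itself as a brief account and says that a separate SAP holds the detail and prevails.

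**The concern.** When randomization is balanced within strata that predict the outcome, a test that ignores the strata counts between-stratum variation as noise. It becomes slightly conservative and loses some power. The protocol gives reasons to expect some prognostic value. Returning patients have already been lost once (2.2.1), clinic-level factors are described as barriers to engagement (2.1.1), and the control arm is each clinic's own standard of care. A similar loss arises when a score measured at entry is not used as a covariate in the follow-up comparison. Because all Cox models are fitted within one arm, the plan also yields no estimate of the hazard ratio between arms, although Table 5 is expressed in hazard ratios.

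What is at stake is efficiency: little for the primary outcome, and possibly more for time to ART, where a larger share of patients may have the event.

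**Working it through.** **1. The plan's own figure.** Inputs from 9.4.1: 150 per arm, two-sided alpha 0.05, 70% (SOC) and 85% (ALERT) free of the endpoint.
- HR = ln(0.70)/ln(0.85) = 2.19, as stated.
- Expected events D = 150 × (0.30 + 0.15) = 67.5, which is 22.5% of 300.
- Freedman form: power = Φ(√67.5 × (2.19 − 1)/(2.19 + 1) − 1.96) = 86.7%, against the stated 87%. The same formula comes within 2 points of every row of Table 5.

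**2. Primary outcome, unstratified against stratified log-rank on the same simulated data.** 300 patients, six strata of 50, arms balanced within strata, exponential times, censoring at week 48, 20,000 runs. Hazards were solved so that the marginal rates stay at 70% and 85%. All stratum effects are assumptions.

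| Assumed effect | Returning HR; site HRs | Hazard spread | Unstratified | Stratified | Gain (points) |
|---|---|---|---|---|---|
| None | 1; 1/1/1 | 1 | 88.1% | 88.1% | 0 |
| Mild | 1.5; 1/1.25/1.5 | 1.5 × 1.5 = 2.25 | 88.8% | 89.0% | +0.2 |
| Moderate | 2; 1/1.5/2 | 2 × 2 = 4 | 88.8% | 89.7% | +0.9 |
| Extreme | 3; 1/2/3 | 3 × 3 = 9 | 89.8% | 91.9% | +2.1 |

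With unequal strata (sites of 150/90/60, 30% returning) the gains are +0.1, +0.2, +1.0 and +2.6. In the 75%/87.5% row of Table 5, moderate effects give +1.1. With no treatment effect and equal strata, the unstratified test rejects in 5.0, 4.8, 4.4 and 3.6% of runs from none to extreme; the stratified test rejects in 5.0 to 5.1%.

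**3. Time to ART.** The plan gives no start rate or effect. Assumed SOC start by week 48 is 56, 70 or 85%. The 56% borrows the figure in 2.1 for eligible patients receiving ART, which is not a start rate after entry. The HRs of 1.5, 1.45 and 1.4 give about 80% power with no stratum effect. The gain depends on what is held fixed as stratum effects grow (equal strata; gains taken before rounding):

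| Held fixed | Effect | SOC start 56% | 70% | 85% |
|---|---|---|---|---|
| Marginal rates | Mild | +1.2 | +1.3 | +1.8 |
| Marginal rates | Moderate | 82.8 to 86.7% (+3.9) | 84.3 to 89.1% (+4.8) | 84.6 to 90.1% (+5.5) |
| Within-stratum HR | Mild | +1.5 | +1.5 | +2.2 |
| Within-stratum HR | Moderate | 73.6 to 78.8% (+5.1) | 73.0 to 79.1% (+6.1) | 69.0 to 76.9% (+7.9) |
| Either | None | −0.3 | −0.7 | −1.2 |

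With a weaker effect (returning HR 1.25, sites 1/1.1/1.25, a spread of about 1.6) the gain is 0.0 for the primary and −0.2 to +0.5 for ART. A separate simulation used permuted blocks of 4, site multipliers k, 1, 1/k, a new/returning HR of k, and a fixed within-stratum HR for ART. At k = 1.25 and 1.5 (spreads k³ = 1.95 and 3.4) it gave +0.5 and +0.6 for the primary, and +0.5 to +1.2 and +3.5 to +5.7 for ART.

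**4. Continuous scores.** With baseline correlation r (assumed), adjustment leaves 1 − r² of the follow-up-only variance. Against a change score the ratio is (1 − r²)/(2(1 − r)) = (1 + r)/2. Starting from an assumed 80% power, power = Φ(2.80/√ratio − 1.96).

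| r | Ratio to follow-up only | 80% becomes | Ratio to change score | 80% becomes |
|---|---|---|---|---|
| 0.3 | 0.91 | 83.6% | 0.65 | 93.5% |
| 0.5 | 0.75 | 89.9% | 0.75 | 89.9% |
| 0.7 | 0.51 | 97.5% | 0.85 | 86.0% |

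**5. Sparse strata.** Expected LTFU events in the smallest stratum are 67.5/6 = 11.2 with equal strata and no effect, 5.6 at moderate and 3.3 at extreme effects. With the unequal sizes above, the smallest stratum has 18 patients and 18 × 0.225 = 4.0 events.

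**The case against.** The strongest reply is that Section 9 is only a summary. Strata in a log-rank test are the kind of detail a full SAP holds, and that SAP prevails. This stands as a limit. A reader might infer that the trial's plan omits stratification altogether; the text supports only that Section 9 does not name it.

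Second, the planned primary test is valid, matches the test used for sizing, and gains at most about 1 point at mild to moderate effects. That is less than the spread between standard formulas for the same design (86.7% by Freedman, 89.8% by Schoenfeld). This also stands. A reader might infer an inflated false-positive rate or an underpowered trial. The check shows neither: type I error is at or below 5% apart from simulation noise, and the 87% reproduces.

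Third, the ART gains rest on assumptions. A reader might take 8 points as the expected loss. That needs a fourfold hazard spread, 85% ART start and a fixed within-stratum HR together. Wider spreads give more (about 11 points at k = 1.75, a 5.4-fold spread), but the documents support no particular spread. With weak strata the gain vanishes.

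Fourth, a stratified hazard ratio is a different quantity from the design's 2.19, baseline ART adherence has little meaning for patients not on treatment, and the plan's Wilcoxon option should not be lost. These objections are right and shape the fix. The descriptive label in 9.6.4 carries less weight, because tests and a significance level are named.

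**Conclusion.** The point holds as an optional improvement of low severity. On the text of Section 9, the analysis ignores the randomization strata, plans no between-arm hazard ratio and does not use baseline as a covariate.

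The size is about 0 to 1 point of primary power. For time to ART it is about 0 to 6 points with marginal rates fixed, and up to about 8 only in the corner case described above. Part of the gain is recovered conservatism: at moderate effects the unstratified ART test rejects in 3.6 to 4.0% of null runs, the stratified test in 5.0 to 5.2%. Score comparisons could gain more, depending on r.

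Stratum effects, stratum sizes, ART start rates and correlations are all assumed. The direction is firm if the strata predict the outcome; the size is not.

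**What to change.** - **9.6.2 and 9.6.3:** stratify both log-rank tests by clinic site and new/returning status. Report the between-arm hazard ratio from a Cox model stratified the same way, and state that it is a within-stratum effect, not directly comparable with the marginal 2.19 in Table 5. Keep the unstratified log-rank test as a sensitivity analysis, because some strata may have few LTFU events.
- **9.6.4:** compare continuous scores and CD4 by linear regression on arm, baseline value and strata where a meaningful baseline exists. Leave out baseline adjustment for ART adherence in patients not on ART at entry. Keep a rank-based fallback if assumptions fail, such as the same model on ranks or the planned Wilcoxon test.
- **If the separate SAP already specifies this,** align Section 9 with it.

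The cost is wording only, since strata and baseline values are already collected. If the strata turn out not to be prognostic, the price is about 0 to 0.1 point of primary power and 0.3 to 1.2 points for time to ART in these runs.

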1.1.2 Secondary hypotheses

- 1.1.2.1 Subjects randomized to the ALERT specialist arm will have higher ART uptake compared to subjects in the SOC arm.
- 1.1.2.2 Use of detailed assessments at study entry will allow for the identification of covariates associated with poor retention and initiation of ART.
- 1.1.2.3 Use of an ALERT specialist and a structured retention module intervention will modify the impact of covariates on retention and initiation of ART.

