1.3 Secondary objectives

- 1.3.1 To evaluate the effect of an ALERT worker on the time to initiation of ART per DHHS guidelines.
- 1.3.2 To assess factors predictive of loss to care, such as demographic, socioeconomic, and psychosocial factors, risk behavior, substance use and psychiatric illness.
- 1.3.3 To assess if the ALERT intervention mitigates the impact of psychosocial barriers on retention in care and initiation of ART.
- 1.3.4 To compare in the intervention vs. SOC arm (assessed at 12 month intervals):
 - 1.3.4.1 Baseline and annual scores on standardized assessments of HIV literacy, disclosure and social support, perception of stigma, barriers to care, ART adherence and Intention to Adhere, Beck Depression Index, substance use evaluations, HIV high-risk

		transmission behaviors, and measures of self-efficacy
	1.3.4.2	Number of visits per year with HIV prescribing provider per year
	1.3.4.3	HIV RNA < 50 and 200 copies/mL at 12 months and every 12 months thereafter
	1.3.4.4	CD4 cell counts and changes from baseline in CD4 at 12 months and every 12 months thereafter
	1.3.4.5	Time to AIDS diagnosis or death
1.3.5		e reasons identified in the refusal survey why patients who are study decline study participation

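### The plan asks whether ALERT changes covariate effects, but section 9.6 fits each arm separately and specifies no comparison of those effects between arms

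*Combined protocol and SAP*

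**What the plan says.** Two different questions appear among the secondary aims.

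- **Prediction.** Hypothesis 1.1.2.2 expects the entry assessments to permit "identification of covariates associated with poor retention and initiation of ART". Objective 1.3.2 is "To assess factors predictive of loss to care".
- **Effect modification.** Hypothesis 1.1.2.3 states that the intervention "will modify the impact of covariates on retention and initiation of ART". Objective 1.3.3 is "To assess if the ALERT intervention mitigates the impact of psychosocial barriers on retention in care and initiation of ART".

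For the covariates, section 9.6.2 plans an analysis "to assess the factors associated with time-to-LTFU", in which "Cox regression models will be performed on two subgroups, looking at each arm separately". Section 9.6.3 repeats this design for time to ART initiation.

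Section 9.6.4 adds: "Descriptive analyses will be conducted for all the secondary analyses including comparisons between randomized groups on the following measures". The list that follows covers literacy and depression scores, visit counts, HIV RNA, CD4 and similar measures. The tests named are Fisher's exact, t and Wilcoxon.

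For secondary analyses in general, section 9.6.1 says "no adjustments for multiple comparisons will be made, and a p-value of 0.05 will be considered statistically significant".

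Section 9.0 describes section 9 as a brief account and gives precedence to a SAP. Beyond section 9.6, no SAP text was available.

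**The concern.** Effect modification is a statement about a contrast: the covariate's hazard ratio under ALERT against its hazard ratio under standard of care (SOC). Section 9.6 produces the two hazard ratios but names nothing that compares them. The stated purpose of the models matches the prediction aim, and the comparisons in 9.6.4 concern levels of measures, not covariate effects.

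This leaves the reading of 1.1.2.3 and 1.3.3 open. The only decision rule in sight is p<0.05 without adjustment. Applied to each arm's model, it would invite the inference that a barrier significant under SOC but not under ALERT has been mitigated. That inference is unsound. Each arm has limited power, and ALERT is expected to have fewer LTFU events, so the pattern can arise when the covariate effect is the same in both arms. The error would tend to favour the trial's own hypothesis.

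**Working it through.** **The plan's own figure.** Section 9.4.1 assumes 150 per arm and event-free rates of 70% (SOC) and 85% (ALERT).

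- Hazard ratio: ln(0.70)/ln(0.85) = 2.195, matching the stated 2.19.
- Expected events: 150 × 0.30 = 45 in SOC and 150 × 0.15 = 22.5 in ALERT, 67.5 in total.
- Power (Freedman): Φ(√67.5 × 1.195/3.195 − 1.96) = 86.7%, matching the stated 87%.

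That figure is sound, but it concerns the overall comparison. The documents give no power for effect modification.

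**Reading each arm by p<0.05 when there is no modification.** Assumptions not in the documents: one binary covariate with prevalence p, and a hazard ratio of 2.0 in both arms. For d events, SE = 1/√(d·p·(1−p)), and power is that of a two-sided Wald test. Then P(significant in SOC only) = power in SOC × (1 − power in ALERT).

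| p | Power SOC | Power ALERT | SOC only, closed form | SOC only, simulated | Interaction test rejects, simulated |
|---|---|---|---|---|---|
| 10% | 0.286 | 0.167 | 24% | 29–31% | 3% |
| 20% | 0.460 | 0.260 | 34% | 36–37% | 4% |
| 30% | 0.568 | 0.325 | 38% | 39–40% | 5% |
| 50% | 0.642 | 0.376 | 40% | 39–42% | 5% |

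The SOC-only ranges span repeated simulations. The interaction column is from 4,000 trials per scenario with exponential times and a single-covariate Cox model in each arm.

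Sensitivity, by closed form:

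- At a hazard ratio of 1.5, the SOC-only pattern occurs in 12% (p = 10%), 17% (20%) and 20–23% (30–50%).
- Across all rows of Table 5 at a hazard ratio of 2.0, it occurs in 18–27%, 28–38% and 34–44% respectively.
- With the 67.5 events split equally (33.75 per arm), it is about 18%, 23% and 25%. Low power within each arm is therefore the main cause, and the unequal events add about 6 to 15 points.

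**What a direct contrast could show.** The SE of the log ratio of hazard ratios is √(1/(45p(1−p)) + 1/(22.5p(1−p))). The 80%-power ratio is exp(2.80 × SE), and the 95% CI factor is exp(1.96 × SE).

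| p | SE | Power for a ratio of 2, closed form | Same, simulated | Ratio for 80% power | 95% CI multiplies or divides by |
|---|---|---|---|---|---|
| 10% | 0.861 | 13% | 4% | 11.2 | 5.4 |
| 20% | 0.645 | 19% | 15% | 6.1 | 3.5 |
| 30% | 0.563 | 23% | 23% | 4.85 | 3.0 |
| 50% | 0.516 | 27% | 26% | 4.25 | 2.75 |

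The simulation used hazard ratios of 2.0 in SOC and 1.0 in ALERT. At 10% prevalence the closed form is too optimistic: about a tenth of simulated trials had an arm hazard ratio that could not be estimated. All closed-form entries in that row should be read with that caution.

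No figure is given for ART initiation because the documents state no ART rates.

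**The case against.** The strongest reply is that the arm-specific models are themselves the intended answer to 1.3.3. That objective says assess, not test. Prediction alone gives no obvious reason to split by arm, and 9.6.4 describes the secondary analyses as descriptive. Since the arms are independent, the contrast follows from the two sets of log hazard ratios and standard errors. This has force: what is missing is the last step, not the data. It does not close the gap, because 1.1.2.3 asserts modification and section 9.6 never says that the estimates will be compared or how.

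Second, section 9.0 defers to a SAP, where an interaction term might well be specified. A reader might infer that no such analysis is planned anywhere. The documents do not support that; the point is confined to section 9.6.

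Third, a reader might infer that the investigators will claim mitigation from significance in one arm only. The plan does not say so. The 24–40% is the price of a reading left open, not an error rate of the stated analysis, and it rests on an assumed hazard ratio and prevalence.

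Fourth, an interaction test has little power here. That is correct. It argues for an exploratory label and an interval, not for leaving the contrast undefined: a wide interval displays the uncertainty that two lists of p-values would hide.

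**Conclusion.** The point holds for section 9.6 as written. A stated secondary hypothesis and objective have arm-specific estimates but no specified estimate, interval or test of the difference they are about, for either retention or ART initiation.

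The illustrative risk of misreading equal effects as mitigation is about 24–40% by closed form (29–42% by simulation) at an assumed hazard ratio of 2.0, and 12–23% by closed form at 1.5. An interaction test rejects in about 3–5% under equal effects of 2.0. These figures assume the 70%/85% design rates and a single binary covariate of prevalence 10–50%. Follow-up beyond 48 weeks may add events. Multivariable models would be less precise: one term for each of the six predictor groups in 9.6.2 leaves 22.5/6 = 3.75 ALERT events per term.

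It would go too far to conclude that naming the contrast lets the trial settle the question. Simulated power for a ratio of 2 is about 22–27% at prevalence 30–50%, 15% at 20% and 4% at 10%. The matter deserves correction but is secondary; the primary log-rank comparison is unaffected.

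**What to change.** For each endpoint, add to section 9.6 a Cox model on all randomized patients with arm, covariate and arm-by-covariate terms. Stratify by, or adjust for, site and newly diagnosed/returning status. Limit it to a short pre-specified list of psychosocial barriers, and say whether each interaction is adjusted for the other predictors.

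Report the ratio of hazard ratios with its 95% CI as the exploratory analysis of 1.1.2.3 and 1.3.3. Keep the arm-specific hazard ratios as descriptive, and state that significance in one arm only is not evidence of effect modification. If the separate SAP already contains such an analysis, align section 9.6 with it.

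The cost is a few sentences; no new data are needed. The drawbacks are real:

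- **Precision.** 80% power needs a ratio of about 4–6 at prevalence 20–50%, so 1.3.3 will probably stay inconclusive.
- **Multiplicity.** With no adjustment, six independent interaction tests, one per predictor group, carry a 1 − 0.95⁶ = 26% chance of at least one false positive. That is why the list should be short.
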